13. SAFETY REPORTING

Definitions

Adverse Event (AE)

An AE or adverse experience is:

Any untoward medical occurrence in a patient or clinical investigation participants, which does not necessarily have to have a causal relationship with this treatment.

An AE can therefore be any unfavourable and unintended sign (including an abnormal laboratory finding), symptom or disease temporally associated with the study, whether or not considered related to the study.

Adverse Reaction (AR)

All untoward and unintended responses related to the study.

All cases judged by either the reporting medically qualified professional or the sponsor as having a reasonable suspected causal relationship to the study qualify as adverse reactions. There are no expected ARs in this study.

Severe Adverse Events

To ensure no confusion or misunderstanding of the difference between the terms "serious" and "severe", which are not synonymous, the following note of clarification is provided:

The term "severe" is often used to describe the intensity (severity) of a specific event (as in mild, moderate, or severe myocardial infarction); the event itself, however, may be of relatively minor medical significance (such as severe headache). This is not the same as "serious," which is based on patient/event outcome or action criteria usually associated with events that pose a threat to a participant's life or functioning. Seriousness (not severity) serves as a guide for defining regulatory reporting obligations.

Serious Adverse Event or Serious Adverse Reaction

A serious adverse event or reaction is any untoward medical occurrence that at any dose:

- Results in death,
- Is life-threatening,

NOTE: The term "life-threatening" in the definition of "serious" refers to an event in which the participant was at risk of death at the time of the event; it does not refer to an event which hypothetically might have caused death if it were more severe.

- Requires inpatient hospitalisation or prolongation of existing hospitalisation,
- Results in persistent or significant disability/incapacity, or

- Is a congenital anomaly/birth defect.
- Other important medical events*

*Other events that may not result in death, are not life threatening, or do not require hospitalisation, may be considered a serious adverse event when, based upon appropriate medical judgement, the event may jeopardise the patient and may require medical or surgical intervention to prevent one of the outcomes listed above.

Expected Serious Adverse Events/Reactions

This study is a non-invasive lifestyle related study and therefore no SAE/Rs are expected.

Suspected Unexpected Serious Adverse Reactions

This study is a non-invasive lifestyle related study and therefore no SUSARs are expected.

Reporting Procedures for All Adverse Events

All AEs occurring during the study observed by investigators or reported by the participant, whether or not attributed to study, will be recorded on the CRF. The following information will be recorded: description, date of onset and end date, severity, assessment of relatedness to study, other suspect device and action taken. Follow-up information should be provided as necessary.

AEs considered related to the study as judged by a medically qualified investigator or the sponsor will be followed until resolution or the event is considered stable. All related AEs that result in a participant's withdrawal from the study or are present at the end of the study, should be followed up until a satisfactory resolution occurs.

Reporting Procedures for Serious Adverse Events

All SAEs must be reported to the Sponsor within one working day of discovery or notification of the event. The Sponsor will perform an initial check of the information and ensure that it is reviewed at the next R&D Management meeting. All SAE information must be recorded on an SAE form and sent to the Sponsor using the appropriate reporting form and the contact details on there. Additional information received for a case (follow-up or corrections to the original case) needs to be detailed on a new SAE form which must be sent to the Sponsor using the appropriate reporting form and the contact details on there.

The Sponsor will report all SUSARs to the Research Ethics Committee concerned. Fatal or life-threatening SUSARs must be reported within 7 days and all other SUSARs within 15 days. The Chief

Investigator will inform all investigators concerned of relevant information about SUSARs that could adversely affect the safety of participants.

In addition to the expedited reporting above, the Chief Investigator shall submit once a year throughout the study or on request an Annual Report to the Ethics Committee which lists all SAEs / SUSARs that have occurred during the preceding 12 months.

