11. STUDY PROCEDURES

Verbal eligibility check

Prior to commencing the study, participants will be contacted via telephone and an initial verbal eligibility check will take place (approx. 30 min conversation). Following this, potentially eligible participants will be invited to visit the Sir Peter Mansfield Imaging Centre for study assessment visit one.

Within 72 hours of each visit to a research site (assessment visits and supervised training sessions), participants will be contacted via telephone by a member of the research team and a verbal COVID-19 symptom screening questionnaire will be administered. As per site guidelines, the questionnaire will be site-specific to Leicester and Nottingham sites. Furthermore, the COVID-19 symptom screening questionnaire will be further completed by participants upon arrival at each study site visit to further screen for symptoms.

Assessment visit 1 - Sir Peter Mansfield Imaging Centre (University of Nottingham)

Informed consent

Before any study related procedure can take place, the participant must sign and date the most recent approved version of the Informed Consent Form. Before consent is obtained the responsible individual will ensure that the participant fully understands all aspects of the study. It will also be clearly stated that the participant is free to withdraw from the study at any time, for any reason, without prejudice to future care, and with no obligation to give the reason for withdrawal. If a participant withdraws from the study but does not withdraw their consent, then data already obtained may be used for the study. If a participant has withdrawn due to an adverse event, a healthcare professional will follow up as appropriate.

The consent form will be signed and dated based up on an informed decision. The consent process will be performed by someone who has received consent training, has been authorised by the Chief Investigator, and is named on the delegation of authority log. The original signed form will be retained at the study site and copy will be given to the participant. A third copy will be posted to the participant's GP.

Questionnaires

Participants will complete several pen and paper based questionnaires to assess their eligibility to participate in the study and to provide baseline study data. These will include the following:

- Physical Activity Readiness Questionnaire - to determine participants' readiness to exercise and/or contraindications

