Participants randomised to control will receive no interventions during the six-week intervention phase. During this time, control participants will be asked to not change any aspects of their lifestyles. Ahead of week five, participants will be posted a physical activity monitor to wear continuously during week five and six. Participants will also complete weighed food diaries during week five (two weekdays and one weekend day).

Participants randomised to exercise training will complete four exercise training sessions per week during the six-week intervention. Each week, at least one session will be supervised by the research team whilst the remaining sessions will consist of participants undertaking brisk walking on their own. All exercise sessions will be composed of continuous moderate-intensity exercise and last 35 - 50 minutes in duration (depending on intervention week). The specific details relating to these training sessions can be seen in section 12 (Table 2).

Assessment visit 3 (post-intervention) - Sir Peter Mansfield Imaging Centre (University of Nottingham)

The assessments undertaken at visit three will be a repeat of those completed during visit one.

Assessment visit 4 (post-intervention) - Leicester General Hospital (Leicester Diabetes Centre) or Queens Medical Centre Hospital (NIHR Nottingham BRC)

The assessments undertaken at visit four will be a repeat of those completed during visit two except that a medical examination will not be performed.

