Participants progressing to Part B of the study (obese men with NAFLD and T2DM/prediabetes) will then be randomised to exercise training or control for six weeks. Participants will be made aware of their group assignment via telephone. Control participants will undergo no interventions and will be asked not to alter any aspect of their lifestyle during the next six weeks. Ahead of week five, control participants will receive a physical activity monitor and food diary in the post to enable them to record their habitual physical activity and food intake during weeks five and six. After the intervention phase has ended, control participants will complete two additional study assessment visits (visits three and four) to obtain post-intervention measurements. These visits will be a repeat of assessment visits one and two (excluding the pre-exercise screening in visit two).

Participants randomised to the exercise training group will complete 24 exercise training sessions (35 to 50 min of moderate-intensity exercise) during the six-week intervention. Four training sessions will be completed each week, with at least one of these sessions being supervised by the study team. Participants will have the option to undergo these sessions at Loughborough University (National Centre of Sport and Exercise Medicine), Nottingham (Queens Medical Centre Hospital) or Leicester (Leicester General Hospital) depending on preference. The remainder of the sessions each week to be completed by participants will be unsupervised sessions of brisk walking which will be recorded via a heart rate monitor and watch. Participants will be supported after each unsupervised session via a telephone call from a member of the research team and the intensity and duration of the session will be recorded from the watch. Participants in the exercise group will wear a wrist-worn movement sensor throughout the entire training phase and will complete weighed food diaries (two week and one weekend day) in the fifth and sixth weeks of training.

Exercise training

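### Adverse events are collected passively while scheduled staff contact in the six weeks is 24 sessions against none, so any description of events by arm is liable to favour control

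*Protocol*

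**What the plan says.** Protocol section 13 (Reporting Procedures for All Adverse Events) says that what goes on the case report form is "All AEs occurring during the study observed by investigators or reported by the participant", whether or not it is attributed to the study. It names no question to be put to participants, no visit at which to ask it and no period to be covered.

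Contact with the exercise arm is set out in section 12 (Overview of procedures). These men "will complete 24 exercise training sessions (35 to 50 min of moderate-intensity exercise) during the six-week intervention". Supervision is set as follows: "Four training sessions will be completed each week, with at least one of these sessions being supervised by the study team". For the rest, "Participants will be supported after each unsupervised session via a telephone call from a member of the research team".

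For the other arm, section 11 (Six week intervention) says: "Participants randomised to control will receive no interventions during the six-week intervention phase". The only scheduled item is in section 12: "Ahead of week five, control participants will receive a physical activity monitor and food diary in the post".

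Two provisions apply to both arms. Section 11 (Verbal eligibility check) ties symptom screening to site visits: within 72 hours of each one, "participants will be contacted via telephone by a member of the research team and a verbal COVID-19 symptom screening questionnaire will be administered", and the questionnaire is repeated on arrival. For the end of the intervention, section 11 says: "The assessments undertaken at visit three will be a repeat of those completed during visit one". Visit 1 includes a health screen questionnaire on medical history and current medication.

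**The concern.** Under passive collection, an event enters the record if staff happen to see it or the man happens to mention it. The arms differ greatly in how often either can happen. An exercise man with a sore knee or a brief illness speaks to staff within a day or two. A control man with the same complaint has no planned occasion to mention it for most of six weeks, and may have forgotten it by then.

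Section 13 defines an adverse event broadly, covering any unfavourable sign or symptom whether related or not, and asks for all of them with onset and end dates. That aim cannot be met equally in the two arms as written. The control arm also supplies the background rate against which events during training are naturally judged. If that background is under-recorded, a table of events by arm can suggest that training caused complaints that were equally common without it. Serious events in controls may also come to light late. No analysis plan can recover events that were never collected.

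**Working it through.** **1. Scheduled contacts during the six weeks**

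Inputs: four sessions a week for six weeks, at least one a week supervised, and a call after each unsupervised session (section 12); no visit or call for controls (sections 9, 11 and 12).

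- Exercise: 4 × 6 = 24 sessions, which reproduces the protocol's figure. At least 1 × 6 = 6 are face to face, and up to 3 × 6 = 18 are followed by a call. Symptom screening around each supervised session comes on top.
- Control: 0. The posted monitor and diary go one way and carry no health enquiry. The next staff contact is the screening call before visit 3.

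**2. Wait from an event to the next scheduled contact**

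Assume that an event is equally likely at any time in 42 days and that sessions are evenly spaced. The mean wait is then half the gap between contacts.

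- Exercise: 42/24 = 1.75 days between contacts; 1.75/2 = 0.875, about 0.9 days.
- Control: 42/2 = 21 days to the end of week six. If contact falls 2 to 3 days later, the wait is 23 to 24 days. The 48 to 72 hour window in section 9 is counted from the last training session, so applying it to controls is an assumption.

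**3. What unequal capture would do to counts (illustration only)**

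The protocol gives neither an event rate nor a capture probability. Suppose the true risk is the same in both arms and staff contact captures 95% of events on exercise. The apparent exercise-to-control ratio is then 0.95 divided by the control capture.

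| Control capture (assumed) | Apparent ratio |
|---|---|
| 80% | 0.95/0.80 = 1.2 |
| 50% | 0.95/0.50 = 1.9 |
| 30% | 0.95/0.30 = 3.2 |

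With 13 men per arm (section 3), an assumed true risk of 0.4 and 50% control capture, the expected numbers recorded are 13 × 0.4 × 0.95 = 4.9 on exercise and 13 × 0.4 × 0.50 = 2.6 on control. Counts this small could fall either way by chance. The table shows a direction, not an estimate.

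**4. Does anything elsewhere even out collection?**

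Visit 3 repeats the visit 1 questionnaires in both arms. Section 11 describes those questionnaires as tools for eligibility and baseline data, and no section assigns them to adverse event collection. The symptom screen reaches controls only around visits 3 and 4.

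**The case against.** The strongest reply is that no comparison of harms is planned. Adverse events are absent from the objectives (section 8) and from the outcomes (section 9), and section 14 contains no analysis of them. Section 13 uses them for individual recording, follow-up and reporting. Neither co-primary result is touched. This stands, and it limits the point to safety recording and to whatever description of events by arm is later given.

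Second, both arms attend visits 3 and 4 and repeat the health questionnaires there, and controls may report an event at any time. This also stands in part: some events would be recovered, so it is too strong to say that events in controls will be missed. But recovery is incidental, because nothing directs staff to use those answers for this purpose.

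Third, the calls after sessions are for support and for recording intensity and duration, not for asking about events. That is correct, and collection is passive in both arms. The exercise men still have many more occasions to mention something, which is all the point needs.

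Fourth, question wording often sits in the case report form or operating procedures, which are not shown, and more contact with a training arm is inherent in the design. Both are fair, but the rule that the protocol does state still makes capture depend on contact.

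A reader might also infer that late knowledge of a serious event in a control man breaks the one-working-day rule. It does not: the clock in section 13 starts at discovery or notification. A late discovery that is promptly reported complies.

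**Conclusion.** The point holds in a limited form. As written, adverse event capture depends on staff contact, and scheduled contact in the six weeks is 24 sessions against none. Minor or transient events in controls are liable to be under-recorded. Serious ones are liable to become known late unless the man reports them: the mean wait to scheduled contact is about 21 days or more, against about 0.9 days on exercise, assuming uniform event times and evenly spaced sessions. Any description of events by arm is therefore liable to favour control.

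It is tempting to go further and say that the trial will show an excess of harm on exercise of some stated size. The documents do not support that. The ratios of 1.2 to 3.2 rest entirely on assumed capture, visit 3 may recover some events, and with 13 men per arm chance could outweigh the bias. This is a cheap improvement to safety recording, not a threat to the primary result.

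**What to change.** Add to section 13, Reporting Procedures for All Adverse Events, text to this effect:

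- At visit 3, every Part B participant is asked the same scripted question about adverse events, covering the period since randomisation.
- Any summary of adverse events by arm uses the answers to that question and states how many men were asked in each arm.
- Events noted at training sessions or in calls after sessions continue to be recorded and reported under the existing rules, and are listed separately.

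A brief call to the 13 controls when the monitor is posted before week five is optional. It would shorten the delay in learning of events, which a question at visit 3 alone does not do.

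The cost is one question at a visit that already takes place, plus 13 short calls if the option is taken. The drawback is recall error over six weeks. Exercise men may remember somewhat better, having talked to staff throughout, so the question greatly reduces the dependence on arm but may not remove it entirely.

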14. STATISTICS

Description of statistical methods

Descriptive statistics will be calculated to outline the characteristics of the study sample. Normality of data will be assessed using histograms and box plots, while further analysis of skewness and kurtosis will be conducted if normality is not clear from the histograms and box plots. Depending on the distribution of data, participant characteristics will be reported as mean (SD) or median (IQR) and number (percentage) for continuous variables and for categorical variables respectively.

For part A of the study, data will be checked for parametric assumptions. Independent samples t-tests will be used to analyse differences in continuous variables between study groups (obese men with NAFLD and obese men with NAFLD and T2DM in part A of the study). To examine factors associated with NAFLD and T2DM, univariate logistic regression models will be performed with NAFLD and T2DM (diabetic individuals with NAFLD vs. non-diabetic individuals with NAFLD) as the dependent variable. All variables significantly associated with NAFLD and T2DM in univariate logistic regression analyses will be included in multivariate logistic regression analysis.

For part B of the study, baseline descriptive statistics will be summarised by treatment arm (Intervention vs control). Data will be checked for parametric assumptions. For the primary outcome, change in hepatic saturated lipid index (%) from baseline to six weeks due to moderate-intensity exercise training in men with NAFLD and T2DM/prediabetes, treatment arms will be compared using linear regression modelling. The analysis will include a binary indicator for randomisation group as the explanatory variable, terms for the stratification category (ethnicity) and adjustments for the baseline measure of the outcome (hepatic saturated lipid index).

Complete case analysis will be utilised for the primary analysis. Intention to treat will be carried out as sensitivity analysis, using multiple imputation for missing values. Secondary outcomes will be analysed using similar methods as the main analysis, with an appropriate model selected dependent on the distribution of the outcome.

The assumptions associated with each model will be assessed and where these are not met alternative models or parameterisations will be considered. A value of $P < 0.05$ will be considered statistically significant for all analyses. Statistical analyses of the baseline data and all future analysis will be carried out using STATA version 15.

The Number of Participants

The sample size for the research outlined in this protocol was undertaken by a statistician in the Leicester Clinical Trials Unit. The sample size calculations were informed by data published in a previous study which validated the method for measuring hepatic fat quality via ¹H-MRS[16].

Part A of this research (cross-sectional analyses) was powered (80%) to detect a difference in the liver saturated fat indices of 0.5 between men with NAFLD with T2DM versus non-diabetic men with NAFLD (alpha 5%, SD 0.4 in each group). 28 participants are needed to provide adequate statistical power for this analysis (14 in each group). Based on the same data, the power calculation showed that 24 participants are needed for Part B of the outlined research (RCT). This is inflated to 26 to allow for expected drop-out (10%).

Please note that the baseline data for all participants entering Part B of this research will be used in Part A and therefore the cross-sectional analyses will include data from 26 men with NAFLD & T2DM and 14 non-diabetic men with NAFLD.

Procedure for dealing with missing and spurious data

Missing data will be replaced using multiple imputation or another appropriate method. In Part B, participants completing less than 85% of all training sessions will not be included in the final analysis.

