Research aims and objectives	
The research outlined in this proposal seeks to determine the impact of T2DM on liver fat quality in patients with NAFLD and to characterise changes in liver fat quality in response to a supervised exercise training programme.
 
The specific objectives of this work are to:
 
• characterise the liver fat phenotype (saturation, unsaturation and polyunsaturation indices) and associated metabolic parameters in obese men with NAFLD and T2DM versus non-diabetic obese men with NAFLD• determine the impact of six weeks supervised exercise training on liver fat quality (saturation, unsaturation and polyunsaturation indices) and associated metabolic parameters in obese men with NAFLD and T2DM/prediabetes.
------------------------------	--

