8. OBJECTIVES

Co-primary objectives

To determine: a) whether differences exist in the liver saturated fat index between obese men with NAFLD, with versus without, T2DM; b) the impact of six weeks exercise training on these outcomes in obese men with NAFLD and T2DM/prediabetes.

Secondary objectives

- To characterise potential differences in the following outcomes between obese men with NAFLD and T2DM versus non-diabetic obese men with NAFLD
 - Liver unsaturated fat index
 - Liver polyunsaturated fat index
 - Total liver fat percentage
 - Liver inflammation
 - Visceral adipose tissue
 - Circulating cardiometabolic biomarkers
 - Circulating liver enzymes
 - Circulating hepatokines
 - Objectively measured sedentary time and physical activity
 - Energy and macronutrient intake
 - Body weight & body fat percentage
 - Blood pressure
 - Aerobic fitness (peak oxygen uptake)
- To determine the impact of six weeks moderate-intensity exercise training on the following outcomes in obese men with NAFLD and T2DM/prediabetes
 - Liver unsaturated fat index
 - Liver polyunsaturated fat index
 - Total liver fat percentage
 - Liver inflammation
 - Visceral adipose tissue
 - Circulating cardiometabolic biomarkers
 - Circulating liver enzymes
 - Circulating hepatokines

- Objectively measured sedentary time and habitual physical activity
- Energy and macronutrient intake
- Body weight and body fat percentage
- Blood pressure
- Aerobic fitness (peak oxygen uptake)

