Participants randomised to control will receive no interventions and will be requested to maintain their habitual lifestyle during the six week intervention phase. Ahead of week five, participants will be posted a wrist worn physical activity monitor to wear continuously for the final two weeks of the study.

Participants will also complete a food diary during this time (two week and one weekend day in week five and six).

Participants randomised to the exercise training intervention will complete 24 moderate-intensity exercise training sessions over the subsequent six weeks (four times per week; ~50 min per session). Each week, at least one of the four exercise training sessions will be supervised by the research team. The remainder of the sessions each week will be unsupervised but monitored objectively using a heart rate monitor. Post- intervention assessments will be completed 48 h - 72 h after the final exercise training session.

After the intervention phase, participants will attend two final assessment sessions to obtain post-intervention data. Assessment visit three will be a repeat of assessment visit one whilst assessment visit four will be a repeat of assessment visit two (minus the medical examination).

[figure not shown]

Figure 1: flow diagram of the study protocol
 SPMIC – Sir Peter Mansfield Imaging Centre; QMC – Queens Medical Centre, Nottingham; LDC – Leicester Diabetes Centre; LU – Loughborough University

Primary and secondary endpoints / outcome measures

Co-primary outcomes: Liver saturated lipid index (%) determined by proton magnetic resonance spectroscopy (¹H-MRS) using a 3T MRI scanner

- 1) Comparison between obese men with NAFLD versus obese men with NAFLD and T2DM (Part A)
- 2) Response to the six week exercise training intervention (Part B)

Secondary outcomes:

- Liver unsaturated lipid index (%) - measured using ¹H-MRS
- Liver polyunsaturated lipid index (%) - measured using ¹H-MRS
- Total hepatic lipid composition (%) - measured using ¹H-MRS
- Liver inflammation - measured using MRI
- Visceral adipose tissue - measured using MRI
- Subcutaneous abdominal adipose tissue - measured using MRI
- Body mass and body fat percentage
- Blood pressure
- Aerobic fitness (peak oxygen uptake)
- Circulating metabolic biomarkers (fasted blood sample)
 - Liver enzymes
 - Glucose
 - Insulin
 - Lipids
 - HbA1c
 - HOMA-IR (surrogate marker of peripheral insulin resistance)
 - ADIPO-IR (surrogate marker of adipose tissue insulin resistance)

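### Part A: every variable with univariate P<0.05 enters the logistic model although the smaller group has 14 men; and, a lesser point, an unadjusted t-test cannot carry the summary's 'impact of T2DM'

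*Protocol*

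**What the plan says.** **Analysis (Protocol, section 14).** For Part A: "Independent samples t-tests will be used to analyse differences in continuous variables between study groups". Univariate logistic models then take diabetes group as the outcome ("diabetic individuals with NAFLD vs. non-diabetic individuals with NAFLD"). The next step is fixed: "All variables significantly associated with NAFLD and T2DM in univariate logistic regression analyses will be included in multivariate logistic regression analysis". The threshold follows from the statement that P<0.05 "will be considered statistically significant for all analyses". No adjusted model with the saturated index as outcome is named for Part A. For Part B the same section does name covariates (ethnicity and the baseline index).

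**Size (section 14).** "the cross-sectional analyses will include data from 26 men with NAFLD & T2DM and 14 non-diabetic men with NAFLD". The design inputs are a difference of 0.5, SD 0.4 in each group, alpha 5% and 80% power, giving 14 per group.

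**Question asked.** Co-primary objective (a) in section 8 is "whether differences exist in the liver saturated fat index between obese men with NAFLD, with versus without, T2DM", and the endpoint list in section 9 likewise calls Part A a comparison. The study summary (section 3) goes further: the research "seeks to determine the impact of T2DM on liver fat quality in patients with NAFLD".

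**Who is compared (section 10).** Shared criteria restrict both groups to non-smoking men with liver fat of at least 5.56%, stable weight and no regular vigorous training. Age may run from 30 to 75 and BMI from 27 to 45 (from 23 if south Asian). The non-diabetic group needs HbA1c below 6%. The other group needs 6.0-10%, may have T2DM or prediabetes, must be treated by lifestyle or metformin only, and must be willing and able to enter Part B.

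**The concern.** The entry rule uses the same 40 men to choose the predictors and then to test them. A variable is in the final model because its P-value was small, so its P-value there no longer has its nominal meaning. With 14 men in the smaller class, a few predictors already strain the model, and the rule sets no limit. At stake is the list of factors reported as associated with T2DM: some may be chance findings and some coefficients may be unstable.

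The second matter is interpretation. If a crude difference in the saturated index is reported as the impact of T2DM, part of it may reflect age, BMI or ethnicity, the admission of men with prediabetes, or the extra entry criteria of that group.

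**Working it through.** **1. The plan's own figure.** Normal approximation, two-sided (sidedness is not stated): n per group = 2(1.96 + 0.8416)² × 0.4²/0.5² = 10.05, so 11. The exact t calculation needs 12 (power 83.3%; 11 gives 79.6%). The stated 14 per group is therefore more than 80% power requires. That is a separate matter and errs on the safe side. For the planned 26 v 14:

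- SE = 0.4 × √(1/26 + 1/14) = 0.1326
- power for 0.5 on 38 df = 95.7%

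Power of the t-test is not the problem.

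**2. Entry rule when nothing differs.** Simulation with 26 v 14, 20 null candidates (assumed), Wald tests, 2,000 runs:

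| Correlation between candidates (assumed) | At least one enters | At least one significant in the multivariable model |
|---|---|---|
| 0 | 54.3% | 50.1% |
| 0.3 | 47.2% | 34.5% |
| 0.5 | 35.5% | 19.7% |

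Two readings follow.

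- Among null variables that enter, about 30% (correlation 0.5) to 76% (correlation 0) are significant in the multivariable model. A valid test would give 5%. This is the effect of the selection.
- The 20-50% in the last column reflects 20 candidates being tested, not the entry rule; the second step lowers the rate. With two candidates at correlation 0/0.5, screening then modelling gives 7.3/6.9%, against 7.9/7.9% when both are prespecified.

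**3. Entry rule when the groups truly differ.** Correlation 0.3 (assumed), 300 runs each; men of the smaller class per variable = 14/k, where k is the mean number entering:

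| Candidates | True difference (assumed) | Mean k | 14/k | Runs with 3 or more entering |
|---|---|---|---|---|
| 10 | 0.5 SD | 2.8 | 5.0 | 48% |
| 10 | 0.8 SD | 6.1 | 2.3 | 91% |
| 20 | 0.5 SD | 5.7 | 2.5 | 72% |
| 20 | 0.8 SD | 12.1 | 1.2 | 99% |

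In the last row the multivariable fit failed or diverged in about 45% of runs; the exact share depends on how failure is defined. For scale, section 9 lists about 24 outcomes by line item before panels are split.

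**4. HbA1c.** Its limits (<6% v 6.0-10%) help define the groups. If the measurement that sets the group is also analysed, the groups separate completely, no finite estimate exists, and the Wald rule never lets it in. With a second measurement of assumed error SD 0.1/0.3/0.5 it enters in 2-9/46-73/82-96% of runs. Either way it restates the group definition and explains nothing.

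**5. The t-test as evidence of impact.** Suppose T2DM has no effect, and one covariate correlates r with the index within groups and differs by k SD between them (both assumed). The spurious difference is r × k × 0.4:

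| r | k | Spurious difference | t-test rejects |
|---|---|---|---|
| 0.1 | 0.25 | 0.01 | 5.1% |
| 0.3 | 0.5 | 0.06 | 7.3% |
| 0.5 | 0.5 | 0.10 | 11.4% |
| 0.3 | 1.0 | 0.12 | 14.3% |
| 0.5 | 1.0 | 0.20 | 31.3% |

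The last four rows are 12-40% of the 0.5 target.

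**6. Price of adjustment.** Three covariates, ethnicity counted as one term: df = 40 - 5 = 35 and SE = 0.1326/√(1 - R²), where R² is the share of group membership that the covariates explain. If they explain none of the index, power for 0.5 at R² = 0, 0.2, 0.4 and 0.5 is 95.6%, 90.6%, 81.1% and 73.7%.

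**The case against.** **The t-test is the right test.** Both the co-primary objective and the endpoint list ask only whether the groups differ. The specific objective beneath the aim in the summary is also descriptive, and section 14 makes no causal claim. This stands. A reader might infer that the co-primary analysis is wrong or that its error rate is inflated; the documents do not support that. The mismatch is with one sentence of the summary.

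**The false-positive rate is multiplicity.** A reader might set 20-50% for 20 screened candidates beside 7-8% for two prespecified ones and blame the entry rule. That compares 20 tests with two. This objection also stands. What it leaves untouched is the distortion of P-values among the variables that enter, and the number that can enter.

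**The confounding is assumed.** True. The Protocol gives no correlation or imbalance, and under weak confounding the rate is 5.1%. The figures show what could happen, not that the comparison is biased.

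**The candidate list belongs in a statistical analysis plan.** Agreed, and its absence is not held against the Protocol. The entry rule itself is written into section 14.

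**Section 14 allows other models where assumptions fail.** A failed fit might trigger that clause. Selection by P-value and confounding are not failures of model assumptions, so it does not reach them.

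**Conclusion.** The point holds in two parts of unequal weight.

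The main one is the entry rule. It is fixed in section 14, it invalidates the P-values of the variables it selects (about 30-76% instead of 5% for null variables that enter), and it can load about 3 to 12 predictors onto 14 men. These sizes rest on assumed candidate counts, correlations and group differences; that P-values chosen this way are not valid does not. The model is secondary and does not adjust the co-primary result. HbA1c should not be a predictor because it helps define the outcome. A reader might infer that it is bound to break the model, but that depends on which measurement is analysed.

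The lesser part is wording and interpretation. The t-test validly answers co-primary (a), but its result cannot be called the impact of T2DM: the groups are not randomised, age and BMI vary widely, and the group labelled T2DM in section 14 admits prediabetes and has its own entry criteria. Adjustment would not justify the word impact either, since it cannot remove those criteria.

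The changes should be made, but neither co-primary test is invalid without them.

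**What to change.** **Section 14, logistic model.** Delete the sentence that enters all univariately significant variables. If the model is kept, label it exploratory, use one or two prespecified predictors or a penalised (Firth) fit, and leave out HbA1c, glucose and indices built from glucose. Cost: fewer factors are examined.

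**Section 14, saturated index.** Keep the unadjusted difference. Add one supportive linear regression of the index on group, adjusted for age, BMI and ethnicity, all already collected at visit 1. Report both as associations. Cost: three degrees of freedom and some precision. Power for 0.5 in the adjusted model stays above the planned 80% up to R² = 0.4 and is 73.7% at 0.5.

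**Section 3, aim.** Replace the reference to the impact of T2DM with a difference between the two groups, and state that one of them includes men with prediabetes. Cost: one sentence.
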